**It may be necessary to skip study drug dosing for the following related adverse event(s):**

Any  $\geq$  Grade 2 non-skin related adverse event (including immune-mediated adverse reactions), except for laboratory abnormalities

Any  $\geq$  Grade 3 laboratory abnormality

Any adverse event, laboratory abnormality or intercurrent illness that, in the judgment of the investigator, presents a substantial clinical risk to the subject with continued dosing.

**It is necessary to skip study drug dosing for the following adverse events:**

Any  $\geq$  Grade 3 skin related adverse event regardless of causality.

**Restart ipilimumab dosing if/when the adverse event(s) resolve(s) to  $\leq$  Grade 1 severity or returns to baseline within 2 weeks of planned dose administration:**

If the *adverse event has resolved*, restart ipilimumab dosing at the next scheduled time point per protocol.

If the adverse event has not resolved in the protocol-specified dosing window (3 weeks [ $\pm 3$  days]), the next scheduled dose will be skipped and dosing will be resumed at the subsequently scheduled dose.

If  $> 1$  dose is expected to be skipped, the dosing schedule modifications must be discussed with the principal investigator prior to implementation.

## **5.4 Discontinuation of Study Therapy**

Subjects **MUST** be discontinued from study therapy AND withdrawn from the study for the following reasons:

Withdrawal of informed consent (subject's decision to withdraw for any reason)

Any clinical adverse event, laboratory abnormality or intercurrent illness which, in the opinion of the investigator, indicates that continued treatment with study therapy is not in the best interest of the subject

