### 3.1.4 Follow-up

- Subjects who are no longer receiving ipilimumab because of unacceptable toxicity (refractory Grade > 3 immune-mediated adverse reactions) or due to investigator judgment are managed in follow-up. Efficacy assessments for these subjects during follow-up are as per the standard of care. Date of death is recorded.
- Subjects who discontinue ipilimumab treatments should be followed until death or the closure of the study (whichever is first).
- Subjects who are no longer receiving ipilimumab because of clinical progression and who have switched to alternative treatment are not followed formally except to record the date of death.

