#### **Permanent Discontinuation of Ipilimumab**

##### ***Permanent Discontinuation for Related Adverse Events***

Permanently discontinue ipilimumab for any of the following:

Persistent moderate adverse reactions or inability to reduce corticosteroid dose to 7.5 mg prednisone or equivalent per day.

Severe or life-threatening adverse reactions, including any of the following:

- Colitis with abdominal pain, fever, ileus, or peritoneal signs; increase in stool frequency (7 or more over baseline), stool incontinence, need for

intravenous hydration for more than 24 hours, gastrointestinal hemorrhage, and gastrointestinal perforation

- Aspartate aminotransferase (AST) or alanine aminotransferase (ALT) >5 times the upper limit of normal or total bilirubin >3 times the upper limit of normal
- Stevens-Johnson syndrome, toxic epidermal necrolysis, or rash complicated by full thickness dermal ulceration, or necrotic, bullous, or hemorrhagic manifestations
- Severe motor or sensory neuropathy, Guillain-Barré syndrome, or myasthenia gravis
- Severe immune-mediated reactions involving any organ system (eg, nephritis, pneumonitis, pancreatitis, non-infectious myocarditis, hypophysitis)
- Immune-mediated ocular disease that is unresponsive to topical immunosuppressive therapy
- Any adverse event, laboratory abnormality or intercurrent illness which, in the judgment of the investigator, presents a substantial clinical risk to the patient with continued dosing.
- The development of progression as defined in the irRC as at least a 25% increase in tumor burden compared with nadir (at any single time point) in 2 consecutive observations at least 4 weeks apart and/or clinical deterioration of

subject's condition such that further benefit from ipilimumab dosing is unlikely or requires a change of therapy at the treating physician's discretion.

Please refer to the IB for specific treatment algorithms.

**The following neurological adverse event requires permanent discontinuation of ipilimumab and defines unacceptable neurotoxicity:**

- Any motor neurologic toxicity  $\geq$  Grade 3 regardless of causality
- Any  $\geq$  Grade 3 treatment related sensory neurologic toxicity

Please refer to the IB for specific treatment algorithms.

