- **Overall response.** All evaluable patients (i.e. eligible patients who have received at least two doses of ipilimumab and SABR) will be assessed in terms of their best response to therapy by both mWHO and irRC. Those who achieve a partial response (PR) or complete response (CR) will be considered responses and the overall response rate will be calculated as the number of PRs and CRs divided by the total number of evaluable patients. Best overall response rate will be reported taking into account all post-treatment imaging.
- **Overall survival and progression-free survival as continuous time-to-event outcomes.** All evaluable patients will be used for this analysis. Kaplan-Meier curves will be used to estimate overall and progression-free survival. Each of these variables is measured from the date of study registration to the date of event (i.e., death or disease progression). In the case of the overall survival endpoint the date of last follow-up is to be used if no event has occurred at their last evaluation. In the case of the progression-free survival endpoint the date of last tumor assessment is to be used if no event has occurred at their last evaluation.
- **Correlative markers:** Several correlative markers will be explored in this trial in relation to clinical outcomes of interest, and in particular in relation to the primary endpoint of 6-month PFS rate. Given the limited overall sample size as well as the relatively limited expected proportion of patients who are progression-free and alive at 6 months, these analyses will be largely exploratory and hypothesis-generating in nature. Markers will be summarized univariately in a quantitative manner and also summarized by clinical outcome group (e.g. prog-free and alive at 6 months vs. not). Graphical analyses will be largely used to assess potential patterns and relationships; e.g. side-by-side boxplots to assess differences in continuous marker levels between those with vs. without the clinical improvement. We may also explore changes in these markers in relation to baseline, with clinical outcome incorporated through use of different plotting characters. Overall, hypothesis testing will largely be avoided given the sample size limitations but we will still obtain important preliminary data that can inform future studies and help better understand the mechanisms of this treatment regimen in this patient population.

*Statistical and Data Analysis:*

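### Section 5.4 makes an investigator-judged adverse event or illness a mandatory exit from the study, contradicting the follow-up in 3.1.4 and 6.10; if 5.4 is followed, overall survival may be censored by toxicity

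*Combined protocol and SAP*

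**What the plan says.** The first list in 5.4 (Discontinuation of Study Therapy) states that subjects must "be discontinued from study therapy AND withdrawn from the study for the following reasons". Besides withdrawn consent, pregnancy, sponsor termination and detention, the list includes any clinical event, laboratory finding or illness that in the investigator's opinion "indicates that continued treatment with study therapy is not in the best interest of the subject".

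Other sections treat the same or nearly the same patients differently:

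- **3.1.4 (Follow-up).** Patients off ipilimumab for unacceptable toxicity or by investigator judgment go into follow-up, and their death is recorded. More generally: "Subjects who discontinue ipilimumab treatments should be followed until death or the closure of the study (whichever is first").
- **6.10 (Efficacy Assessments).** Patients who leave protocol because of toxicity after SABR still have re-staging scans. Those who never reach SABR because of early toxicity need not.
- **4.5.1.** Withdrawal for an unacceptable adverse event is a right of the investigator, not an obligation. An end-of-study visit is to be completed at withdrawal.
- **4.5.2.** Follow-up after withdrawal depends on what the withdrawing subject says he or she wishes.
- **5.3 and the second list in 5.4.** A similar trigger leads only to a possible skipped dose ("presents a substantial clinical risk to the subject with continued dosing") or to permanent discontinuation of ipilimumab ("presents a substantial clinical risk to the patient with continued dosing"). Neither mentions leaving the study.

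For the analysis, 7.2 says: "In the case of the overall survival endpoint the date of last follow-up is to be used if no event has occurred". For progression-free survival (PFS) the censoring date is the last tumor assessment. Both curves use evaluable patients, meaning those with at least two ipilimumab doses and SABR.

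**The concern.** Stopping treatment and leaving a trial are different events, and the first list in 5.4 joins them. A site that obeys it ends data collection when a patient stops for toxicity or illness. A site that obeys 3.1.4 follows the same patient to death.

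Under the first reading, the last follow-up date used for OS in 7.2 is the withdrawal date. Censoring then depends on a clinical event that is plausibly related to prognosis, whereas the Kaplan-Meier method assumes that it is not. The plan has no analysis that allows for this, and follow-up that was never collected cannot be restored later. OS is a secondary endpoint, so what is at stake is the accuracy of a descriptive curve and the completeness of later follow-up in a few patients.

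**Working it through.** **1. The plan's own figures.** The plan gives no figure for loss to follow-up or for OS precision. Its one efficacy design calculation is for 6-month PFS: success with at least 8 of 32, rates of 15% against 35%, and both errors limited to 10%. Exact binomial tails reproduce it: P(X ≥ 8 | 32, 0.15) = 0.096 and P(X ≥ 8 | 32, 0.35) = 0.918. This point leaves that rule alone, provided that the scans required by 6.10 are done.

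**2. The passages side by side, for a patient stopped after SABR for an investigator-judged adverse event.**

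| Section | Status of the patient | Data after stopping |
|---|---|---|
| 5.4, first list | off therapy and off study, mandatory | not stated |
| 3.1.4 | off ipilimumab, in follow-up | followed to death or study closure |
| 6.10 | off protocol | re-staging scans required |
| 4.5.1 | withdrawal at the investigator's option | withdrawal visit |
| 4.5.2 | subject withdrawing from the intervention | visits continue if the subject agrees |

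The first row cannot be reconciled with the second and third, or its obligation with the option in the fourth. The fifth does not settle the matter, because it turns on the subject's own wish and does not clearly cover a withdrawal imposed by the investigator.

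**3. Who is exposed.** Patients stopped before SABR are outside the evaluable set whatever 5.4 says. The added effect is therefore confined to patients withdrawn after SABR in weeks 5-6. Such withdrawals are plausible, since 1.5.2 places the usual onset of immune-related events 3 to 10 weeks after the first dose.

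- Discontinuation for adverse reactions, phase 3 trial at 3 mg/kg (1.5.2): 10%. 32 × 0.10 = 3.2, about 3 patients. This is an upper figure at that rate, because some of the 10% may stop before SABR.
- Severe to fatal immune-mediated reactions, ipilimumab alone (Table 2): 15%. 32 × 0.15 = 4.8, about 5 patients. This counts reactions, not withdrawals.

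Both rates are for ipilimumab without SABR; the documents give none for the combination.

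**4. Effect on 12-month OS (illustration).** Inputs: median 10 months (1.2, ipilimumab-treated patients), so h = ln 2 / 10 = 0.0693 per month. Assumptions: exponential survival; a share f withdrawn and censored at month 2; the same hazard for all up to then; afterwards the withdrawn patients' hazard is HR × h with HR from 0.5 to 2; no other censoring.

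- Estimate with these patients censored: exp(−2h) × exp(−10h) = 0.8706 × 0.5 = 0.435.
- True value: (1 − f) × exp(−12h) + f × exp(−2h − 10 × HR × h). The last exponential is 0.616 for HR 0.5 and 0.218 for HR 2.

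| Withdrawn | HR | True 12-month OS | Estimate minus truth |
|---|---|---|---|
| 3 of 32 | 0.5 | 0.906 × 0.435 + 0.094 × 0.616 = 0.452 | −1.7 points |
| 3 of 32 | 2 | 0.906 × 0.435 + 0.094 × 0.218 = 0.415 | +2.0 points |
| 5 of 32 | 0.5 | 0.844 × 0.435 + 0.156 × 0.616 = 0.463 | −2.8 points |
| 5 of 32 | 2 | 0.844 × 0.435 + 0.156 × 0.218 = 0.401 | +3.4 points |

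A cruder check gives the same order. With 15% withdrawn early, 12-month OS of 50% in the others and 30% to 60% in the withdrawn, the error lies between 0.15 × (50 − 30) = +3.0 points and 0.15 × (50 − 60) = −1.5 points.

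**5. Comparison with sampling error.** With 32 patients and OS near 0.435, the 95% half-width is 1.96 × √(0.435 × 0.565 / 32) = 0.17, about 17 points.

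**The case against.** The strongest reply is that the protocol already provides for these patients. Section 3.1.4 names those stopped for toxicity or investigator judgment, 6.10 requires their scans after SABR, and 11.1 seeks vital status even when authorization is revoked. Section 4.5.2 covers withdrawn subjects and follows directly on a list that mixes patient and investigator withdrawals. On that view nothing is lost unless staff prefer 5.4 to all of these. OS is secondary with no planned test, and a shift of 2 points is small beside a half-width of about 17.

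Much of this stands. It makes the loss conditional and the effect small. It does not remove the contradiction: 5.4 is worded as mandatory and states no exception.

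A reader might infer several stronger points that the documents do not support:

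- **That survival data are certain to be lost and the curves biased.** The outcome depends on which section is followed, and the calculated error spans zero.
- **That PFS imaging after SABR is lost.** Section 6.10 largely protects it.
- **That about 12 of 32 patients are exposed.** In the phase 3 trial 61% received all four doses, and 39% of 32 is 12.5. That counts missed doses for any reason, which is not the trigger in 5.4.
- **That 4.5.1 imposes the same rule, or that progression forces study exit.** Section 4.5.1 is permissive, and progression falls under the second list in 5.4, which stops ipilimumab only.
- **That safety follow-up collapses.** Serious events are collected for 70 days after dosing stops and followed to resolution or stabilization (10.3.1), later related ones should be reported, and nonserious events that cause discontinuation require follow-up (10.3.3). Appendix II schedules adverse event evaluation to 90 days for everyone.

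**Conclusion.** The contradiction is real and should be corrected. The mandatory study withdrawal in 5.4 conflicts with 3.1.4 and 6.10 and with the optional withdrawal in 4.5.1. If 5.4 is followed, OS may be censored at withdrawal in patients selected by toxicity or illness. The main exposure is OS and later follow-up in patients withdrawn after SABR.

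The likely size is modest: at most about 3 of 32 patients at the 10% rate, and about 2 points on 12-month OS in either direction; about 3 points with 5 patients. These figures rest on the assumed 10-month median, withdrawal at month 2 and a hazard ratio of 0.5 to 2, and on rates for ipilimumab alone. The direction cannot be known from the documents. The case for correction is that the change is cheap and that uncollected follow-up cannot be recovered at analysis.

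**What to change.** Reconcile 5.4, 4.5.1 and 3.1.4 so that stopping study therapy is separate from ending data collection:

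1. In the first list of 5.4, state for the adverse-event and illness item that the subject stops study therapy and remains in follow-up under 3.1.4 and 6.10 unless consent for follow-up is withdrawn. Leave the pregnancy, detention and sponsor-termination items as they are.
2. In 4.5.1, make the same distinction, and align the end-of-study visit named there with the visit in 6.6.1. No visit of that name appears in 6.5 or Appendix II, and 6.6.1 asks only for the reason for withdrawal and for adverse events.
3. In 4.5.2, state that it also covers discontinuation initiated by the investigator.

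The overlapping triggers in 5.3 and the two lists of 5.4 should be reconciled by the sponsor. When a dose is skipped or treatment is stopped is a clinical matter that this point does not address.

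The cost is amendment wording. Survival follow-up and the follow-up visits are already planned in 3.1.4 and Appendix II, and the scans after SABR in 6.10.

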#### Pregnancy

- All WOCBP should be instructed to contact the investigator immediately if they suspect they might be pregnant (e.g., missed or late menstrual period) at any time during study participation. Institutional policy and local regulations should determine the frequency of on study pregnancy tests for WOCBP enrolled in the study.
- The investigator must immediately notify BMS in the event of a confirmed pregnancy in a patient participating in the study.

Termination of the study by Bristol-Myers Squibb (BMS).

Imprisonment or the compulsory detention for treatment of either a psychiatric or physical (e.g., infectious disease) illness.

#### **Permanent Discontinuation of Ipilimumab**

##### ***Permanent Discontinuation for Related Adverse Events***

Permanently discontinue ipilimumab for any of the following:

Persistent moderate adverse reactions or inability to reduce corticosteroid dose to 7.5 mg prednisone or equivalent per day.

Severe or life-threatening adverse reactions, including any of the following:

- Colitis with abdominal pain, fever, ileus, or peritoneal signs; increase in stool frequency (7 or more over baseline), stool incontinence, need for

intravenous hydration for more than 24 hours, gastrointestinal hemorrhage, and gastrointestinal perforation

- Aspartate aminotransferase (AST) or alanine aminotransferase (ALT) >5 times the upper limit of normal or total bilirubin >3 times the upper limit of normal
- Stevens-Johnson syndrome, toxic epidermal necrolysis, or rash complicated by full thickness dermal ulceration, or necrotic, bullous, or hemorrhagic manifestations
- Severe motor or sensory neuropathy, Guillain-Barré syndrome, or myasthenia gravis
- Severe immune-mediated reactions involving any organ system (eg, nephritis, pneumonitis, pancreatitis, non-infectious myocarditis, hypophysitis)
- Immune-mediated ocular disease that is unresponsive to topical immunosuppressive therapy
- Any adverse event, laboratory abnormality or intercurrent illness which, in the judgment of the investigator, presents a substantial clinical risk to the patient with continued dosing.
- The development of progression as defined in the irRC as at least a 25% increase in tumor burden compared with nadir (at any single time point) in 2 consecutive observations at least 4 weeks apart and/or clinical deterioration of

subject's condition such that further benefit from ipilimumab dosing is unlikely or requires a change of therapy at the treating physician's discretion.

Please refer to the IB for specific treatment algorithms.

**The following neurological adverse event requires permanent discontinuation of ipilimumab and defines unacceptable neurotoxicity:**

- Any motor neurologic toxicity  $\geq$  Grade 3 regardless of causality
- Any  $\geq$  Grade 3 treatment related sensory neurologic toxicity

Please refer to the IB for specific treatment algorithms.

***Exceptions to Permanent Discontinuation***

Potentially reversible inflammation ( $<$  Grade 4), attributable to a local anti-tumor reaction and a potential therapeutic response. This includes inflammatory reactions at sites of tumor resections or in draining lymph nodes, or at sites suspicious for, but not diagnostic of metastasis.

Hospitalization for  $\leq$  Grade 2 adverse events where the primary reason for hospitalization is to expedite the clinical work-up.

Patients with the following conditions where in the investigator's opinion continuing study drug administration is justified:

- Ocular toxicity that has responded to topical therapy.
- Endocrinopathies where clinical symptoms are controlled with appropriate hormone replacement therapy. **Note:** Ipilimumab may not be restarted while the patient is being treated with systemic corticosteroids except for patients on stable doses of hormone replacement therapy such as hydrocortisone.

**5.5 Immune-Related Adverse Events (irAEs) Reactions and Immune-mediated Adverse Reactions: Definition, Monitoring, and Treatment**

Blocking CTLA-4 function may permit the emergence of auto-reactive T cells and resultant clinical autoimmunity. Rash/vitiligo, diarrhea/colitis, uveitis/episcleritis, hepatitis, and hypopituitarism were drug-related, presumptive autoimmune events,

now termed immune-mediated adverse reactions, noted in previous ipilimumab studies.

For the purposes of this study, an immune-related adverse reaction is defined as an adverse reaction of unknown etiology associated with drug exposure and consistent with an immune phenomenon. Efforts should be made to rule out neoplastic, infectious, metabolic, toxin or other etiologic causes prior to labeling an event an immune-related adverse reactions. Serologic, immunologic, and histologic (biopsy) data should be used to support the diagnosis of an immune-related toxicity. Suspected immune-related adverse reactions must be documented on an AE or SAE form. Another term for an irAE is an immune-mediate adverse reaction, as it is termed in the Ipilimumab US Prescribing Information. Both terms may be used in this protocol document.

Patients should be informed of and carefully monitored for evidence of clinically significant systemic immune-mediated adverse reactions (e.g., systemic lupus erythematosus-like diseases) or organ-specific immune-mediated adverse reaction (e.g., rash, colitis, uveitis, hepatitis or thyroid disease). If an immune-mediated adverse reaction is noted, appropriate work-up (including biopsy if possible) should be performed, and steroid therapy may be considered if clinically necessary.

It is unknown if systemic corticosteroid therapy has an attenuating effect on ipilimumab activity. However, clinical anti-tumor responses have been maintained in patients treated with corticosteroids and discontinued from ipilimumab. If utilized, corticosteroid therapy should be individualized for each patient. Prior experience suggests that colitis manifested as  $\geq$  Grade 3 diarrhea requires corticosteroid treatment.

Specific treatment algorithms for immune-mediated adverse reactions adverse events are included as appendices in the IB.

## **Other Guidance**

### ***Treatment of Infusion Reactions Associated with Ipilimumab***

Since ipilimumab contains only human protein sequences, it is less likely that any allergic reaction will be seen in patients. However, it is possible that infusion of ipilimumab will induce a cytokine release syndrome that could be evidenced by fever, chills, rigors, rash, pruritus, hypotension, hypertension, bronchospasm, or other symptoms. No prophylactic pre-medication will be given unless indicated by

previous experience in an individual patient. Reactions should be treated based upon the following recommendations.

-For mild symptoms (e.g., localized cutaneous reactions such as mild pruritus, flushing, rash):

- Decrease the rate of infusion until recovery from symptoms, remain at bedside and monitor patient.
- Complete the ipilimumab infusion at the initial planned rate.
- Diphenhydramine 50 mg IV may be administered at the discretion of the treating physician and patients may receive additional doses with close monitoring.
- Premedication with diphenhydramine may be given at the discretion of the investigator for subsequent doses of ipilimumab.

-For moderate symptoms (any symptom not listed above [mild symptoms] or below [severe symptoms] such as generalized pruritus, flushing, rash, dyspnea, hypotension with systolic BP >80 mmHg):

- Interrupt ipilimumab.
- Administer diphenhydramine 50 mg IV.
- Monitor patient closely until resolution of symptoms.
- Corticosteroids may abrogate any beneficial immunologic effect, but may be administered at the discretion of the treating physician.
- Resume ipilimumab infusion after recovery of symptoms.
- At the discretion of the treating physician, ipilimumab infusion may be resumed at *one half the initial infusion rate, then increased incrementally to the initial infusion rate.*
- If symptoms develop after resumption of the infusion, the infusion should be discontinued and no additional ipilimumab should be administered that day.
- The next dose of ipilimumab will be administered at its next scheduled time and may be given with pre-medication (diphenhydramine and

acetaminophen) and careful monitoring, following the same treatment guidelines outlined above.

- At the discretion of the treating physician additional oral or IV antihistamine may be administered prior to dosing with ipilimumab.

-For severe symptoms (e.g., any reaction such as bronchospasm, generalized urticaria, systolic blood pressure <80 mm Hg, or angioedema):

- Immediately discontinue infusion of ipilimumab, and disconnect infusion tubing from the subject.

- Consider bronchodilators, epinephrine 1 mg IV or subcutaneously, and/or diphenhydramine 50 mg IV, with solumedrol 100 mg IV, as needed.

- Patients should be monitored until the investigator is comfortable that the symptoms will not recur.

- No further ipilimumab will be administered.

In case of late-occurring hypersensitivity symptoms (e.g., appearance within one week after treatment of a localized or generalized pruritus), symptomatic treatment may be given (e.g., oral antihistamine, or corticosteroids).

